5.4 DRUG CONCENTRATION MEASUREMENTS AND PHARMACOKINETICS

Exact time points of plasma sampling will be documented in the CRFs by the medical personnel or sent as electronic files to the trial data manager. The actual sampling times will be used for determination of pharmacokinetic parameters.

PK sampling times and periods may be adapted during the trial based on information obtained during trial conduct (e.g. preliminary PK data) including addition of samples and visits as long as the total blood volume taken per subject does not exceed 500 mL. Such changes would be implemented via non-substantial CTP Amendments.

5.4.1 Assessment of Pharmacokinetics

Pharmacokinetic endpoints are listed in [section 5.1](#). Further details will be given in the TSAP.

5.4.2 Methods of sample collection

5.4.2.1 Plasma sampling for pharmacokinetic analysis

For quantification of BI 443651 plasma concentrations, 4.0 mL of blood will be taken from an antecubital or forearm vein into a K-EDTA (potassium ethylenediaminetetraacetic acid) anticoagulant blood drawing tube at the times indicated in [Flow Chart I](#) & [Flow Chart II](#). Blood will be withdrawn by means of either an indwelling venous catheter or by venipuncture with a metal needle.

The K-EDTA-anticoagulated blood samples will be centrifuged for about 10 min at about 2000 g to 4000 g and at 4 to 8 °C. Two plasma aliquots will be obtained and stored in

polypropylene (PP) tubes. The first aliquot should contain at least 1.0 mL plasma, the second aliquot will contain the remaining plasma. The process from blood collection until transfer of plasma aliquots into the freezer should be completed within 90 min. Immediately after centrifugation the samples should be pipetted and put into the freezer. For each aliquot the time when the sample was placed in the freezer will be documented.

The plasma samples have to be stored at about -20°C or below at the clinical site until shipment on dry ice to the logistic CRO. They will also be stored at about -20°C or below at the logistic CRO and the analytical laboratory until analysis. Further details on sample collection, preparation of plasma aliquots, sample handling, and shipping are provided in the lab manual.

At a minimum, the sample tube labels should list the following information: BI trial number, subject number, visit, and planned sampling time. Further information such as matrix and analyte may also be provided.

After completion of the trial the plasma samples may be used for further methodological investigations, e.g. for stability testing, assessment of metabolites. However, only data related to the analyte and/or its metabolite(s) including anti-drug antibodies (if applicable) will be generated by these additional investigations. The study samples will be discarded after completion of the additional investigations but not later than 5 years upon the final study report has been signed.

5.4.3 Analytical determinations

BI 443651 concentrations in plasma

will be determined by validated LC-MS/MS

(liquid chromatography tandem mass spectrometry) assays. All details of the analytical methods will be available prior to the start of sample analysis. Analyses will be performed at Drug Metabolism & Pharmacokinetics Germany, Boehringer Ingelheim Pharma GmbH & Co. KG, Biberach, Germany.

As described in [Section 4.1.5](#), the bioanalyst will be unblinded during sample analysis..

5.4.4 Pharmacokinetic – Pharmacodynamic Relationship

If applicable, an exploratory PK-PD analysis may be undertaken.

5.5 ASSESSMENT OF BIOMARKER(S)

This section is not applicable.

5.7 APPROPRIATENESS OF MEASUREMENTS

The primary and secondary endpoints are standard and accepted for evaluation of safety, tolerability, and PK of an inhaled drug, and are widely used in this kind of studies.

The PK parameters and measurements outlined in [Section 7.3.5](#) are generally used as measurements to assess drug exposure.

All measurements performed during this trial are standard measurements and will be performed in order to monitor safety aspects and to determine PK parameters in an appropriate way.

Therefore, overall, all measurements applied in this trial are considered by the sponsor to be appropriate.

6. INVESTIGATIONAL PLAN

6.1 VISIT SCHEDULE

Exact times of measurements outside the permitted time windows will be documented. The acceptable time windows are given in [Flow Chart I](#) & [Flow Chart II](#).

Study measurements and assessments scheduled to occur 'before' trial medication administration on the main PK sampling days - Day 1, Day 7 and Day 14 - are to be performed and completed within 180 mins prior to drug administration.

The acceptable deviation from the scheduled time for vital signs, ECG, lung function testing and laboratory tests will be ± 15 min during the 2 hours after the first drug administration on the main PK sampling days (Day 1, Day 7 and Day 14) and ± 45 min for vital signs, ECG, lung function testing and laboratory tests at all other time points.

Pre-dose blood samples for PK will be taken from 15 minutes prior to dosing. The acceptable deviation from the scheduled time for PK sampling on the main PK sampling days (Day 1, Day 7 & Day 14) will be ± 5 min during the 4 hours after the first drug administration, ± 10 min from 4h to 8h and ± 15 min from 8h to 12h. On all other days, the acceptable deviation from the scheduled time for PK sampling will be ± 15 min.

The tolerance for drug administration will be the following:

- ± 30 min on Days 1 and 7
- ± 30 min on Day 14 for CF subjects
- ± 45 min on all other treatment days.

If scheduled in [Flow Chart I](#) & [Flow Chart II](#) at the same time as a meal, blood sampling and vital signs, the 12- lead ECG recordings have to be done first. In general, if several measurements including venepuncture are scheduled for the same time, venepuncture should be on the time-point of the measurements, and lung function will be the last procedure due to its inconvenience to the patient and possible influence on physiologic parameters (see [section 5.3.4](#)).

For planned individual plasma concentration sampling times refer to [Flow Chart I](#) & [Flow Chart II](#). While these nominal times should be adhered to as closely as possible, the actual sampling times will be recorded and used for determination of pharmacokinetic parameters.

If a volunteer/subject misses an appointment, it will be rescheduled if possible. Relevant time violations will be identified and their handling discussed no later than at the Report Planning Meeting.

6.2 DETAILS OF TRIAL PROCEDURES AT SELECTED VISITS

6.2.1 Screening and run-in period(s)

After having been informed about the trial, all subjects will give their written informed consent in accordance with GCP and local legislation prior to enrolment in the study.

For information regarding laboratory tests (including drug and virus screening), ECG, vital signs, and physical examination, refer to [Sections 5.3.1](#) to [5.3.8](#).

6.2.2 Treatment period(s)

Each subject will receive the respective trial medication (BI 443651 or placebo b.i.d.) at Day 1 until Day 6 for healthy volunteers, and Day 13 for CF subjects, and then one dose of the respective trial medication (BI 443651 or placebo) in the morning of the final day. CF subjects will undergo subsequent washout period of at least 30 days prior to an additional two weeks of respective trial medication i.e. the alternative medication administered during the first treatment period.

Trial medication will be administered by each subject (under direct supervision, whilst in-clinic of the investigator or his designee). Details on treatments and procedures of administration are described in [Section 4.1.4](#).

All healthy volunteers and CF subjects will attend the trial site, as per [Flow Chart I & Flow Chart II](#), after formal assessment and confirmation of their fitness by the investigator or designee. On all other study days, the study will be performed in an ambulatory fashion (at home / ex-clinic).

For details on time points and procedures for collection of plasma samples for PK analysis, refer to [Flow Chart I & Flow Chart II](#).

The safety measurements performed during the treatment period are specified in [Section 5.2](#) of this protocol and in [Flow Chart I & Flow Chart II](#). For details on time points for all other trial procedures, refer to [Flow Chart I & Flow Chart II](#). AEs and concomitant therapy will be assessed continuously from screening until the end of trial examination.

6.2.3 End of Trial Period

For AE assessment, laboratory tests, recording of ECG and vital signs, physical examination, weight and pregnancy test for female subjects of child bearing potential, during the end of trial period, [see Sections 5.3.1](#) to [5.3.7](#).

Subjects who discontinue treatment before the end of the planned treatment period should undergo the follow-up and end of trial visit.

All abnormal values (including laboratory parameters) that are judged clinically relevant by the investigator will be monitored using the appropriate tests until a return to a medically acceptable level is achieved. Adverse events persisting after trial completion must be monitored until they have normalised or have been sufficiently characterised.

7. STATISTICAL METHODS AND DETERMINATION OF SAMPLE SIZE

7.1 STATISTICAL DESIGN - MODEL

7.1.1 Objectives

Part 1 (MRD): The primary objective is to investigate safety, and tolerability of orally inhaled administration of BI 443651 for 6.5 days b.i.d, in healthy male and female volunteers following administration of 100 µg b.i.d., 400 µg b.i.d., 1200 µg b.i.d. and 1800 b.i.d. µg.

Part 2 (cross-over): The primary objective is to investigate the safety and tolerability of orally inhaled administration of BI 443651 in stable male and female CF subjects following administration of repeated doses of 600 µg b.i.d. BI 443651 over 13.5 days.

For both parts, the primary safety endpoint is defined in [Section 5.1.1](#). Inferential statistics are not planned (as explained in [Section 7.2](#)).

The secondary objective for part 1 is the exploration of the pharmacokinetics of BI 443651 after multiple dosing.

PK endpoints as specified in [Section 5.1](#) will be analysed by descriptive statistics.

Secondary PK endpoints as defined in [Section 5.1.2](#) will be subjected to analysis of dose proportionality by use of the power model for part 1 of this trial.

7.2 NULL AND ALTERNATIVE HYPOTHESES

Safety and tolerability of 5 groups of 5 different dose levels of BI 443651 are to be determined on the basis of the investigated parameters in comparison to placebo. It is not planned to test any statistical hypotheses with regard to these variables in a confirmatory sense. Instead, they will be described in their entirety and evaluated by descriptive statistical methods.

For both trial parts, confidence intervals will be computed and will have to be interpreted in the perspective of the exploratory character of the study, i.e. confidence intervals are considered as interval estimates for effects.

7.3 PLANNED ANALYSES

The statistical analysis will be based on the following analysis sets.

- Enrolled set (ES): This subject set includes subjects that signed informed consent and underwent screening procedures.
- Randomized set (RS): This subject set includes all randomised subjects, whether treated or not.
- Treated set (TS): The treated set includes all subjects who were randomized and treated with at least one dose of study drug. The treatment assignment will be determined based on the first treatment the subjects received.

- Pharmacokinetic set (PKS): The PK parameter analysis set (PKS) includes all subjects in the Treated Set (TS) who provide at least one PK parameter that was not excluded according to the description in [Section 7.3.2](#). Excluded subjects will be listed with their individual plasma concentrations and individual pharmacokinetic parameters, however, will not be included in descriptive statistics for plasma concentrations, pharmacokinetic parameters or other statistical assessment.

All individual data will be listed.

Adherence to the protocol (such as inclusion/exclusion criteria, times of measurement, compliance with intake of trial medication, treatment dispensing errors, prohibited concomitant medication, completeness and consistency of data) will be checked. Important protocol violations (IPVs) will be identified no later than in the Blinded Report Planning Meeting and pre-defined in the TSAP.

7.3.1 Primary endpoint analyses

Analysis of safety and tolerability is described in [Section 7.3.4](#).

7.3.2 Secondary endpoint analyses

The secondary PK parameters (refer to [Section 5.1.2](#)) will be calculated according to the BI Standard Operating Procedure (SOP) ‘Standards and processes for analyses performed within Clinical Pharmacokinetics/Pharmacodynamics’ ([001-MCS-36-472](#), current version). Analyses will be performed for parent drug.

Plasma concentration data and parameters of a subject will be included in the statistical pharmacokinetic (PK) analyses if they are not flagged for exclusion due to a protocol violation relevant to the evaluation of PK (to be decided no later than in the Blinded Report Planning Meeting) or due to PK non-evaluability (as revealed during data analysis, based on the criteria specified below). Exclusion of a subject’s data will be documented in the CTR.

Relevant protocol violations may be

Proprietary confidential information © 2017 Boehringer Ingelheim International GmbH or one or more of its affiliated companies

- Incorrect trial medication taken, i.e. the subject received at least one dose of trial medication the subject was not assigned to
- Incorrect dose of trial medication taken
- Use of restricted medications.

Plasma concentrations and/or parameters of a subject will be considered as non-evaluable, if for example missing samples/concentration data occur at important phases of the PK disposition curve.

Assessment of dose proportionality (Part 1 only)

Dose proportionality will be assessed using the secondary pharmacokinetic endpoints after the first dose AUC_{0-12} , C_{max} and after the last dose $AUC_{\tau,ss}$, $C_{max,ss}$ as specified in [Section 5.1.2](#) for HV.

The basic model for the investigation of dose proportionality will be a power model that describes the functional relationship between the dose and PK endpoints.

$$\exp(Y_{ij}) = \alpha' * \exp(X_i)^\beta * \varepsilon'_{ij}$$

The model consists of a regression model applied to log-transformed data. The corresponding ANCOVA model includes the logarithm of the dose as a covariate.

Together with $\alpha' = \exp(\alpha)$ and $\varepsilon'_{ij} = \exp(\varepsilon_{ij})$, taking natural logarithms converts this model to a linear form as follows:

$$Y_{ij} = \alpha + \beta * X_i + \varepsilon_{ij}$$

where

Y_{ij} logarithm of the pharmacokinetic endpoint for subject j at dose level i;
where $i = 1, \dots, 4, j = 1, \dots, 8$ for HV

α intercept parameter;

β slope parameter;

X_i logarithm of dose i;

ε_{ij} random error associated with subject j at dose level i (assumed to be independent and identically normally distributed).

This equation can be fit as a linear regression model.

Based on the estimate for slope parameter (β), a 2-sided 95% CI for the slope will be computed. Perfect dose proportionality would correspond to a slope of 1. The assumption of a linear relationship between the log-transformed pharmacokinetic endpoint and the log-transformed dose will be checked.

If dose proportionality over the entire dose range investigated cannot be shown, an attempt will be made to identify dose range(s), where dose proportionality can be assumed.

For further details refer to the TSAP (such as selection of covariance structure and comparison of time points).

7.3.4 Safety analyses

Safety will be assessed for the endpoints and parameters of interest listed in [Section 5.1.1](#) and [5.1.3](#) based on the treated set. Safety analyses (except of ECG data) will be descriptive in nature and will be based on BI standards.

Treatments will be compared in a descriptive way. The control group for HV in the safety evaluation will consist of all placebo treated subjects, regardless of the dose group in which they were treated. For CF, each subject will appear in the active treatment group and the placebo group, due to the cross-over structure. The active treatment groups will be compared to the respective placebo group in a descriptive way. Tabulations of frequencies/proportions will be used for the evaluation of categorical (qualitative) data, and tabulations of descriptive statistics will be used to analyse continuous (quantitative) data.

The analyses will be done by 'randomised treatment'.

Measurements (such as ECG, vital signs, or laboratory parameters) or AEs will be assigned to treatments ([see Section 4.1](#)) based on the actual treatment at the planned time of the measurement or on the recorded time of AE onset (concept of treatment emergent AEs).

Therefore, measurements planned or AEs recorded prior to first intake of trial medication will be assigned to 'screening', those between first trial medication intake until next intake or the end of REP will be assigned to the preceding treatment, and all AEs occurring between the end of REP and next treatment intake or trial termination date respectively will be assigned to 'follow-up'. In case of two or more treatments, the follow-up will be summarized according to the previous treatment. These assignments including the corresponding time intervals will be defined in detail in the TSAP. Please note that AEs occurring after the last per protocol contact but entered before database lock will be reported to drug safety only and will not be captured in the trial database.

Adverse events that start before first drug intake and deteriorate under treatment will also be considered as 'treatment emergent'.

Additionally, further treatment intervals (analysing treatments) may be defined in order to provide summary statistics for time intervals, such as combined treatments, on-treatment totals or periods without treatment effects (such as screening and follow-up intervals).

Adverse events will be coded using the Medical Dictionary for Regulatory Activities (MedDRA). Frequency, intensity and causal relationship of AEs will be tabulated by treatment, primary system organ class and preferred term. SAEs, AESIs ([see Section 5.3.10.1](#)) and other significant AEs (according to ICH E3) will be listed separately.

Laboratory data will be analysed both quantitatively as well as qualitatively. The latter will be done via comparison of laboratory data to their reference ranges. Values outside the reference range as well as values defined as clinically relevant will be highlighted in the listings. Treatment groups will be compared descriptively with regard to distribution parameters as well as with regard to frequency and percentage of subjects with abnormal values or clinically relevant abnormal values.

Vital signs, physical examinations, or other safety-relevant data observed at screening, baseline, during the course of the trial, follow-up period and at the end of trial evaluation will be assessed with regard to possible changes compared to findings before start of treatment. Baseline refers to the last measurement before drug administration.

The ECG variables QT, HR, QTcF, QTcB, PR, QRS, and RR obtained from the centralised evaluation of 12-lead ECG recordings will be the basis for the derivation of quantitative and categorical ECG endpoints. These endpoints and their analyses will be described in the TSAP.

7.3.5 Pharmacokinetic and pharmacodynamic analyses

The pharmacokinetic parameters listed in [Section 5.1](#) for BI 443651 will be calculated according to the BI SOP ‘Standards and processes for analyses performed within Clinical Pharmacokinetics/Pharmacodynamics’ ([001-MCS-36-472](#)).

Subjects who are not included in the PKS (refer to [Section 7.3](#)) will be reported with their individual plasma / urine concentrations and individual pharmacokinetic parameters; however, they will not be included in descriptive statistics for plasma concentrations, pharmacokinetic parameters or other statistical assessment.

Only concentration values within the validated concentration range and actual sampling times will be used for the calculation of pharmacokinetic parameters. Concentrations used in the pharmacokinetic calculations will be in the same format provided in the bioanalytical report, (that is, to the same number of decimal places provided in the bioanalytical report). If applicable, PK/PD analyses will be conducted.

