| | | Visit | Day | | | | | | | | | | | | |
| | | | | Planned Time relative to first drug administration [h:min] | | Planned Time relative to a.m. drug administration (at corresponding day) [h:min] | | Approximate clock time (actual day) [h:min] | | Event and comment | | Safety Laboratory ³ | | PK _{blood} | |
| Period 1 / 2 – Two identical periods with a wash-out of at least 30 days | SCR | 1 | -21 to -3 | | | | | | screening ¹ | | X ^{19,22} | | | | |
| | | 2 / 3 | -7 to -3 ²⁵ | | | 08:00 | in-clinic visit, device training¹⁷, allow home | | | | X ^{4,19} | | | | |
| | | | 1 | -01:00 | -01:00 | 07:00 | in-clinic visit | | | | X ^{19,22,24} | | X ²¹ | | |
| | | | | -00:30 | -00:30 | 07:30 | | | | | | | | | X X X |
| | | | | -00:15 | -00:15 | 07:45 | randomisation¹⁵ | | | | X ² | | | | X |
| | | | | 00:00 | 00:00 | 08:00 | drug administration ⁷ , 250 mL water intake | | | | | | | | X |
| | | | | 00:05 | 00:05 | 08:05 | | | | | | | | | X X |
| | | | | 00:15 | 00:15 | 08:15 | | | | | | | | | |
| | | | | 00:30 | 00:30 | 08:30 | | | | X X | | | | X X X | |
| | | | | 00:45 | 00:45 | 08:45 | device instruction ¹⁷ | | | X | | | | | X |
| | | | | 01:00 | 01:00 | 09:00 | | | | | | | | X X X | |
| | | | | 02:00 | 02:00 | 10:00 | 250 mL water intake, thereafter, breakfast ¹² allow home | | | | | | | X X X | |
| | | | 2 to 6 | | | 12:00 | 12:00 | 20:00 | drug administration | | | | | X ²⁰ | |
| | | | | | | 00:00 | 08:00 | drug administration | | | | | | X ²⁰ | X ¹⁴ |
| | | | | | | 12:00 | 20:00 | drug administration | | | | | | X ²⁰ | X ¹⁴ |

FLOW CHART II – CF SUBJECTS (cont.)

| Period 1 / 2 – Two identical periods with a wash-out of at least 30 days between drug administration | | Period | |
|--|-----------------|--|--|
| | | Visit | Day |
| | | Planned Time relative to first drug administration [h:min] | Planned Time relative to first drug administration [h:min] |
| | | 143:00 | -01:00 |
| | | 143:30 | -00:30 |
| | | 143:45 | -00:15 |
| | | 144:00 | 00:00 |
| | | 144:30 | 00:30 |
| | | 156:00 | 12:00 |
| 2 / 3 | 7 (+/- 2 days) | 07:00 | in-clinic visit |
| | | 07:30 | |
| | 8 to 13 | 07:45 | |
| | | 08:00 | device instruction ¹⁷ , drug administration ⁷ , |
| | 14 (-1/+3 days) | 08:30 | allow home |
| | | 20:00 | drug administration |
| | 23 (+/- 2 days) | 00:00 | drug administration |
| | | 12:00 | drug administration |
| | 30 (+/- 5 days) | 07:00 | in-clinic visit |
| | | 07:30 | |
| | 311:00 | 07:45 | |
| | | 08:00 | drug administration ⁷ , 250 mL water intake |

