5. VARIABLES AND THEIR ASSESSMENT

5.1 TRIAL ENDPOINTS

All endpoints listed below apply for both parts of the trial.

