5.1.2 Secondary Endpoint(s)

The following pharmacokinetic parameters will be determined if feasible for healthy volunteers in Part 1

After the first dose on Day 1:

- C_{\max} (maximum measured concentration of the analyte in plasma)
- AUC_{0-12} (area under the concentration-time curve of the analyte in plasma until 12 h after the first dose)

After the last dose on Day 7 (:

- $C_{\max,ss}$ (maximum measured concentration of the analyte in plasma at steady state over a uniform dosing interval τ)
- $AUC_{\tau,ss}$ (area under the concentration-time curve of the analyte in plasma at steady state over a uniform dosing interval τ)

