6.3 PATIENT SETS ANALYSED

The statistical analysis will be based on the following analysis set:

- Enrolled set (ES): all subjects who signed informed consent and underwent screening procedures
- Randomized set (RS): all randomised subjects, whether treated or not
- Treated set (TS): all subjects who were randomized and treated with at least one dose of study drug (active or placebo). The treatment assignment (for CF part: within each treatment period) will be determined based on the first treatment the subjects received.
- Pharmacokinetic set (PKS): all HVs in the TS who provide at least one PK parameter that was not excluded according to the description in Section 7.3.2 of the CTP. Excluded subjects will be listed with their individual plasma concentrations and individual pharmacokinetic parameters, however, will not be included in descriptive statistics for plasma concentrations, pharmacokinetic parameters or other statistical assessment.

Table 6.3: 1 Analysis Sets

Class of endpoint	Analysis Set				
	ES	RS	TS	PKS	
Disposition	X				
Exposure			X		
iPDs		X			
Demographic/baseline endpoints			X		
Safety endpoints			X		
Secondary PK endpoints				X	
Further PK endpoints				X	

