7.5.2 Secondary endpoints

According to CTP Version 8.0 secondary endpoints are only defined for HV and not for CF subjects.

The analysis of secondary endpoints will be based on the PKS.

Dose proportionality of secondary endpoints (AUC_{0-12} , C_{max} , $AUC_{t,13}$, $C_{max,13}$ for HV) over the entire dose range will be evaluated as defined in the CTP, Section 7.3.2, by use of the power

model for healthy volunteers. For each of the secondary endpoints tables displaying geometric means of pairwise ratios together with 95% confidence intervals will be provided by dose group. A summary of results of the power model as described in the CTP, Section 7.3.2 will be displayed by a table. The relationship between the dose and the respective PK parameters will additionally be visualized graphically.

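### Does the exclusion sentence in protocol 7.3.5 bar summaries of the CF plasma concentrations?

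*Protocol*

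**What the plan says.** Protocol 7.3.5 addresses "Subjects who are not included in the PKS". It has their individual values reported and then states: "however, they will not be included in descriptive statistics for plasma concentrations, pharmacokinetic parameters or other statistical assessment". The visible text makes no exception for Part 2.

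Membership of the PKS is defined twice. Under protocol 7.3 the set "includes all subjects in the Treated Set (TS) who provide at least one PK parameter that was not excluded" on the criteria of 7.3.2. SAP 6.3 is narrower: "all HVs in the TS who provide at least one PK parameter that was not excluded".

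The visible PK parameters belong to Part 1. Protocol 5.1.2 begins "The following pharmacokinetic parameters will be determined if feasible for healthy volunteers in Part 1". Section 5.1 says generally "All endpoints listed below apply for both parts of the trial", but SAP 7.5.2 settles the matter for secondary endpoints: "According to CTP Version 8.0 secondary endpoints are only defined for HV and not for CF subjects".

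CF PK is nevertheless planned. Protocol 2.1 announces a sparse PK investigation in CF subjects, and 3.2 counts sparse PK among the things for which 24 CF subjects are considered enough.

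**The concern.** Put in sequence, the sentences seem to cancel a planned analysis. A subject outside the PKS may not be summarised, the SAP's PKS holds only healthy volunteers, and CF subjects are not healthy volunteers. One analyst could follow 7.3.5 to the letter and produce listings only for CF. Another could follow SAP 7 and produce summary tables by time point. If the choice were truly open, the content of the CF concentration tables would be settled after the data were seen, and part of the stated purpose of Part 2 would rest on an unspecified set.

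**Working it through.** No power, alpha or sample-size figure is involved. The check is whether the sentences, read together, give the result that 7.3.5 gives alone.

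1. **Reach of the sentence alone.** Under SAP 6.3 the number of CF subjects in the PKS is 0 of 24 planned. With 40 healthy volunteers and 24 CF subjects, 24 / (40 + 24) = 24 / 64 = 37.5% of planned subjects would be barred from concentration summaries. Under the protocol 7.3 wording the bar depends on whether a CF subject has any PK parameter. None is visible in the current text. SAP 3 says the first CF subjects were recruited under Version 7.0, so some could have one, but the documents do not say how many.

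2. **Whom 7.3.5 describes.** It says these subjects are reported with their individual concentrations and their individual PK parameters. That fits someone who had parameters and was taken out of the set. It does not fit a CF subject for whom no parameter is defined. The sentence also points to Section 7.3. There the matching restriction starts from excluded subjects, meaning those removed under the 7.3.2 criteria. SAP 6.3 repeats it in that form. Read with its own cross-reference, 7.3.5 restates the 7.3 rule.

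3. **The inclusion rule.** Protocol 7.3.2 takes a subject's concentrations and parameters into the statistical PK analyses unless they are flagged for a relevant protocol violation or for non-evaluability. It sets no condition of PKS membership or of having a parameter. Its heading concerns secondary endpoints, which limits its weight for CF, but it is the only visible rule on when a concentration is left out.

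4. **The SAP's general rule.** SAP 7 opens by saying that it covers both populations. It then adds the arithmetic CV, geometric mean and geometric CV for plasma concentrations, with no visible limit to healthy volunteers.

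5. **Intent.** The protocol's entry for amendment 7, which produced Version 8.0, lists the reduced CF sampling: 3 samples on Day 1, 2 on Day 7 and 3 on Day 14, so 3 + 2 + 3 = 8 per period, plus 1 at end of study. It says CF parameters were dropped because they could no longer be calculated, and that CF concentrations would be listed by time point with descriptive statistics. An amendment log is not operative text, so this counts only as evidence of what was meant. On that point it is clear.

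6. **What cannot be seen.** That entry names protocol 5.1.3 among the sections changed. In the public copy 5.1.3 shows only safety criteria, and protocol 7.3.3 is absent. The SAP goes from 5.2.2 to 5.3.2, from 6.3 to 6.5 and from 7.5.2 to 7.6.1. SAP Table 6.3:1 appears to have an unlabelled column after the PKS. These are the places where a set or display for CF concentrations would stand.

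Steps 2 to 5 all point to summarising CF concentrations. Only the opening words of 7.3.5, taken without their cross-reference, point the other way.

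**The case for a change.** The strongest reply is that 7.3.5 turns on PKS membership and nothing else, so a set for CF concentrations named in the removed text would still sit beside a sentence forbidding its use. SAP Table 6.3:1 adds to this: it assigns both secondary and further PK endpoints to the PKS. If CF concentrations count as a further PK endpoint, the visible table sends them to a set with no CF subject in it. Aligning one sentence before final database lock would cost almost nothing and need no new data.

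The wording point stands. The opening of 7.3.5 is wider than the parallel sentences in protocol 7.3 and SAP 6.3, and a tidier text would use the same term in all three places. The predicted consequence does not stand. An analyst working from the whole plan has an exclusion rule based on flagged data, a SAP section that calls for concentration statistics, and a stated intention to summarise CF by time point. The reading of the table depends on how the removed rows or columns classify CF concentrations, which cannot be judged here. Any added line in SAP 6.3 would also depend on that unseen text and might duplicate it.

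**Conclusion.** No change to the plan is needed. This is a loosely worded sentence that its own cross-reference and the surrounding text resolve. Its nominal reach is 24 of 64 planned subjects. The practical stake is whether exploratory CF concentration tables carry summary rows, since individual values are reported either way. The primary endpoint is the frequency of subjects with treatment-emergent adverse events on the treated set, and the secondary PK endpoints are confined to healthy volunteers. Neither depends on this sentence.

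The conclusion rests on two assumptions: that analysts read 7.3.5 together with 7.3, 7.3.2 and SAP 7, and that the text missing from the public copies does not direct the opposite. The second cannot be verified from these copies, but the amendment 7 entry makes it likely.
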